10.6.4 Analysis Plan

All patients who receive treatment will be included in the safety analysis. The number and percentage of patients in the test and control groups will be displayed in a 2x2 table. If the propensity score adjustment is adequate and there is not heterogeneity across study sites, the univariate test will be done as follows: the differences will be computed within each propensity stratum and the test will be done using the method of Mehrota and Railkar using

¹⁸Rosenbaum P and Rubin D. Reducing bias in observational studies using subclassification on the propensity score. J Am Statist Assoc 1984;79:516-24.

¹⁹Cochran W. The planning of observational studies of human populations. J Royal Statistical Society, Series A 1965;128:234-55.

²⁰Cochran W. The effectiveness of adjustment by subclassification in removing bias in observational studies. Biometrics 1968;24:205-13.

the minimum risk weighting factor to obtain the z-statistic.²¹ The z-statistic for this univariate test is provided in the formula below.

$$z = \frac{\widehat{\delta} - (3/16) \left(\sum_{i=1}^5 \frac{n_{ic} n_{it}}{n_{ic} + n_{ic}} \right)}{\sqrt{\sum_{i=1}^5 w_i^2 V_0(\widehat{\delta}_i)}}$$

Where

$$\widehat{\delta} = \left(\sum_{i=1}^5 w_i \widehat{\delta}_i \right),$$

$$w_i = \frac{V_i^{-1}}{\sum_{k=1}^5 V_k^{-1}} \left(\frac{\left(\delta_i \sum_{k=1}^5 V_k^{-1} \right) V_i^{-1}}{\sum_{k=1}^5 V_k^{-1}} \right) \left(\frac{\sum_{k=1}^5 \delta_k V_k^{-1}}{\sum_{k=1}^5 V_k^{-1}} \right),$$

$$\delta_k = p_{tk} - p_{ck},$$

$$V_k = \frac{p_{tk}(1-p_{tk})}{n_{tk}} + \frac{p_{ck}(1-p_{ck})}{n_{ck}},$$

$p_{ik} = x_{ik}/n_{ik}$, x_{ik} is the number of patients with MAE in treatment i in stratum k , n_{ik} is the number of patients in treatment group i and stratum k , and $V_0(\delta_i)$ is the variance of the difference in the proportions for stratum i under the null hypothesis. The formulas in Mehrotra and Railkar include the theoretical δ , but for simplicity the formulas above have been presented with estimates under the null hypothesis ($\delta=0$) which is appropriate for the test statistic to be used in this study.

If there is heterogeneity among the study sites the test will be additionally adjusted for site differences by the method of Fleiss (1993). If the data from the study sites cannot be pooled to form a common estimate of the treatment effect, the following analysis from Fleiss (1993) will be done. Within each stratum i and treatment group j , the mean proportions across study sites is given by the following formula:

$$\bar{p}_{ij} = \frac{\sum_k W_{ijk} p_{ijk}}{\sum_k W_{ijk}}$$

Where p_{ijk} is the estimated MAE proportion from stratum i and site k for treatment j , and $W_{ijk} = 1/((1/n_{ijk})p_{ijk}(1-p_{ijk}))$. for $i=1-5$, $j = T$ for test and C for Control and k is the site number. The

²¹Mehrotra D. and Railkar R. Minimum risk weights for comparing treatments in stratified binomial trials. *Statistics in Medicine* 2000;19:811-25

differences of the weighted proportions will be computed within each propensity stratum and the test will be done using the method of Mehrota and Railkar using the minimum risk weighting factor. The formula for z is the same as above except that the within stratum estimates of the difference are the given by the following,

$$\delta_k = \bar{p}_{tk} - \bar{p}_{ck}$$

Where \bar{p}_{ik} is given by the formula above. The variance within the stratum of the difference is given by the following.

$$V_i = \left(\sum_{k=1}^{m_t} W_{itk} \right)^{-1} + \left(\sum_{k=1}^{m_c} W_{ick} \right)^{-1}$$

Where m_t is the number of sites in the treated sample and m_c is the number of sites in the control sample.

If the P-value from either test above is less than a one-sided 0.025, then the null hypothesis for this analysis will be rejected in favor of the alternative indicating that the new patients have a statistically significantly smaller rate of MAE than the historical surgical control group.

A descriptive analysis and a Kaplan-Meier analysis of the MAE composite at 30 days will be presented. The descriptive analysis will present the rates for the composite MAE and each individual adverse event that is part of the composite with corresponding 95% exact confidence intervals.

To determine those factors that may be associated with MAE, a supportive covariate analyses will be performed by logistic regression to determine if there are differences in the rates among groups when adjusted for other factors. Covariates for these analyses will be age, gender, ASA class, cardiac/coronary artery disease (a composite variable to include arrhythmia, CHF, prior MI, CABG/PCI, heart valve repair/replacement), histories of cancer, cerebrovascular disease, coagulopathy, COPD, diabetes, hypertension, liver disease, peripheral arterial occlusive disease, renal failure, smoking, selected aneurysm characteristics, propensity class (numerical classification of the stratum based on patient's propensity score), plus any variables found to be out of balance in the comparability analyses. Because there is no exact congruence of study sites between the test and control groups it is not possible to account for study site in this analysis. To observe the effect of study site, a multivariable analysis will be done only in the test patients to determine if the study site remains a significant influence to the rate of MAE when other covariates are included in the analysis. Often the differences in study site responses are the result of differences in baseline characteristics the patients at that site such that when a model includes both the study site effect and the covariates effect, the study site no longer retains statistical significance.

If it is not possible to break the data into classes that provide adequate coverage of both treatment groups in each stratum, an alternative primary safety test will be done against a performance goal of 56% derived from the Society for Vascular Surgery (SVS) major adverse

events outcomes for infrarenal open surgical control patients.²² This is reasonably conservative as a performance goal. To this point, a recent publication finds that the rates of these major adverse events are similar between open infrarenal aneurysm repair and open complex aneurysm repair (juxtarenal, pararenal, suprarenal), with the exception of bleeding and renal events, which were significantly higher with open complex aneurysm repair.²³

The null and alternative hypotheses are provided below.

$$H_0: P_t \geq 0.56$$

versus

$$H_1: P_t < 0.56$$

where P_t is the MAE rate at 30 days in the test group

If there is not heterogeneity in the study site MAE rates for the test patients, the univariate test will be done with the exact binomial distribution to determine if the frequency of MAE in the test group is statistically significantly less than 0.56. The formula for this test is provided below.

$$P(X \leq x_t | 0.56) = \sum_{k=1}^{x_t} \binom{n_t}{k} 0.56^k 0.44^{n_t-k} < 0.025$$

Where x_t is the number of test group patients experiencing an MAE and n_t is the number of patients in the test group. If the above expression holds for the observed x_t , the null hypothesis will be rejected and the alternative hypothesis will be accepted.

If there is heterogeneity among the study sites in MAE response, the analysis will be done by the method of Fleiss (1993). The test statistic will be given by the following formula.

$$z = \frac{(\bar{p}_T - 0.56)}{SE(\bar{p}_T)}$$

Where the formula for the weighted estimate of the proportion is given by the following formula.

²²Turnbull I, Criado FJ, Sanchez L, et al. Five year results for the Talent enhanced low profile system abdominal stent graft pivotal trial including early and long term safety and efficacy. J Vasc Surg 2010; 51:537-44.

²³Jeyabalan G, Park T, Rhee RY, et al. Comparison of modern open infrarenal and pararenal abdominal aortic aneurysm repair on early outcomes and renal dysfunction at one year. J Vasc Surg 2011;54:654-9.

$$\bar{p}_T = \frac{\sum_k W_k p_{Tk}}{\sum_k W_k}$$

And the formula for the weight in site k is given by the following

$$W_k = \frac{1}{n_k} p_k (1 - p_k)$$

And the formula for the standard error is given by the following.

$$SE(\bar{p}_T) = \left(\sum_{k=1}^{m_T} W_{Tk} \right)^{-1/2}$$

If the z has a P-value less than a one-sided alpha of 0.025, the null will be rejected and the alternative will be accepted.

Similar to the strategy employed above, to determine those factors that may be associated with MAE, a supportive covariate analyses will be performed by logistic regression to determine if there are differences in the rates among groups when adjusted for other factors in the test group only. Covariates for these analyses will be age, gender, ASA class, cardiac/coronary artery disease (a composite variable to include arrhythmia, CHF, prior MI, CABG/PCI, heart valve repair/replacement), histories of cancer, cerebrovascular disease, coagulopathy, COPD, diabetes, hypertension, liver disease, peripheral arterial occlusive disease, renal failure, smoking, maximum aneurysm diameter, and study site. The final model will be reduced by backward elimination until no covariate terms remain in the model with a P-value less than 0.05.

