4.3. TRIAL DESIGN

This is a multicenter, prospective, single arm clinical trial. Patients with JAA/PAA who are suitable candidates for endovascular repair using the Endologix Fenestrated Stent Graft System will be considered for enrollment.

After this protocol and the patient informed consent form are reviewed and approved by the local Ethics Committee or responsible Institutional Review Board, potential patients will be offered participation in the study. This will be accomplished through the patient's reading of the informed consent form in the patient's native language and discussion of the study with the patient by the investigator and site personnel. Agreement to participate and to attend all follow-up visits will be documented with the patient's signature on the informed consent form, with appropriate signatures of the site investigator and an impartial witness.

After providing written informed consent, screening and eligibility determinations will be performed. Patients will undergo a high resolution, contrast-enhanced computed tomography angiography (CT) scan of the relevant aortic and aortoiliac vasculature within three months of the scheduled procedure. Evaluation of the aortic and vascular anatomy suitability per this protocol, as depicted on the CT scan, will be performed by the site investigator and by an independent core laboratory. Other tests include a physical examination, review of patient medical history for exclusionary conditions, selected blood chemistry and hematology analyses, and ankle-brachial index determination.

Upon acceptance for enrollment, patients will be scheduled for the endovascular repair procedure.

Note: An investigational site may not enroll more than 20% of the total Trial Phase enrollment.

Following patient discharge from the hospital, the first follow-up visit will be made at one month (± 2 weeks). A CT scan will be performed to assess aneurysm morphology and device integrity and patency, as well as the status of the renal arteries and implanted stent grafts. Subsequent follow-up will be made at six months, one year, and annually to five years.

Continued patient follow-up beyond five years is outside of the scope of this study. Nonetheless, all patients should be monitored and evaluated per the institutional standards of care for patients who receive an endovascular stent graft.

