10.4 BASELINE COMPARABILITY ANALYSIS

A set of important demographic or prognostic variables will be compared across trial sites to determine homogeneity of trial sites in terms of baseline patient characteristics. Factors found to differ significantly by trial site will identify that variable or trial site as a possible covariate in subsequent analyses.

In the analysis of comparability of trial sites, it is anticipated that a small number of sites may have a patient enrollment that is too small to allow meaningful statistical analysis. To allow the inclusion of sites with this condition, small sites will be combined into one pseudo-site the size of which will not exceed the size of the largest trial site. It is not possible to determine the number of patients below which this aggregation will occur until after enrollment is completed, but generally trial sites with four or fewer patients may be combined.

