10.5 POOLING

Data pooling incorporates two factors: combination of data across trial sites and the actual method of obtaining an estimate of the endpoint from combined data. Data will be combined from multiple trial sites for the trial analyses. The justification for this pooling is made on a clinical basis with three critical factors: The basis for pooling comes from: 1) The trial sites must implement one common protocol; 2) The sponsor must provide very close monitoring of study site compliance; and, 3) the trial sites must use common data collection procedures.¹⁶

In order to determine if there is a similar response across the sites to allow the responses to be pooled in the trial the primary safety and effectiveness proportions will be tested for homogeneity by logistic regression using a univariate model of study site within the test group. If the P-value for study site is less than 0.15, differences in study site proportions in response will be assumed to exist and the overall estimate of the proportion in the test patients will be obtained by taking a weighted average of the proportions at each site with the weight being the inverse of the variance of the proportion at that

¹⁶Meinert C. Clinical Trials: Design, Conduct, and Analysis. 1986; Oxford University Press. New York, NY

site.¹⁷ The sum of these weighted proportions divided by the sum of the weights will be the overall estimate for the study. For the safety variable, the differences of the weighted proportions will form the basis of the statistical test and for the effectiveness variable, the overall weighted proportions will be the basis of the test. The test of significance in these circumstances are fully described below.

If the heterogeneity P-value is greater than 0.15, an analysis of the primary effectiveness endpoint by the Fleiss (1993) method will be done.

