Significant main effect or interactions from this analysis will be evidence of imbalance. For categorical covariates, this analysis will be done with logistic regression. With the logistic regression analyses, the output Chi-square values will be examined. The maneuvers to be attempted if adequate balance is not achieved by the initial propensity model include reducing the model by removing non-significant covariates and adding higher order terms for significant covariates to the propensity model to see if the resulting propensity score assignments improve the balance. After each propensity adjustment, the same balance analyses will be done.

If an adequate degree of adjustment cannot be achieved using quintiles because of sparse representation of the test or control groups in a given stratum (less than two patients to allow estimation of the variance for continuous or ordinal covariates), the analysis will be attempted by using quartiles. If the data are still too sparse, tertiles will be used. While dividing the data into quintiles accounts for about 90% of the bias in measured variables, quartiles accounts for about 85% bias reduction, and tertiles account for about 80% bias reduction.^{19,20}

The sole rationale for acceptability of the degree of adjustment will be based on the F-statistics for continuous or ordinal covariates or the chi-square statistics for categorical covariates.¹⁷

If significant imbalance remains, the analysis involving the control group will be abandoned and an alternative analysis of the performance goal discussed in §10.6.4 will be used as the primary safety analysis.

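### The site-adjusted primary safety test has no value when any stratum-by-site cell has 0% or 100% MAE, which with quintiles is almost certain

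*Combined protocol and SAP*

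**What the plan says.** Section 10.5 tests whether MAE rates differ between sites by logistic regression, "using a univariate model of study site within the test group". It continues: "If the P-value for study site is less than 0.15", site differences are taken to exist, and the overall proportion becomes a weighted average over sites, "with the weight being the inverse of the variance of the proportion at that" site.

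Section 10.6.4 carries this into the comparison with the 66 surgical controls. Within each propensity stratum i and arm j, the site-k cell has weight "W_{ijk} = 1/((1/n_{ijk})p_{ijk}(1-p_{ijk" (closing brackets follow). The within-stratum variance is the sum over the two arms of the reciprocal of the summed weights, so the controls are split by site as well. The decision rule begins "If the P-value from either test above is less than a one-sided 0.025".

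Three other provisions might be expected to help:

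- Section 10.6.3 moves from quintiles to quartiles or tertiles "because of sparse representation of the test or control groups in a given stratum".
- Sections 10.6.3 and 10.6.4 fall back to a 56% performance goal if balance or stratum coverage fails.
- Section 10.4, on baseline comparability, says "small sites will be combined into one pseudo-site the size of which will not exceed the size of the largest trial site".

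**The concern.** A cell with p = 0 or p = 1 has an estimated variance of zero, so its inverse-variance weight divides by zero. The weighted mean is then infinity over infinity, and that arm's contribution to the stratum variance is zero. A one-patient cell always does this. The wording of 10.5 and the formula in 10.6.4 agree, so this is not a matter of how the equation was read from the page.

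None of the three provisions looks at stratum-by-site cells. The quartile/tertile rule counts patients of an arm within a stratum. The performance-goal fallback depends on stratum-level balance or coverage. The pseudo-site rule is written for another purpose and cannot merge sites into fewer, larger groups than the enrollment cap allows.

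At stake is whether the confirmatory safety test is fixed in advance. If the branch is entered and the statistic has no value, someone must choose a repair with the MAE outcomes in hand.

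**Working it through.** **Inputs.** Test group 97 (section 5.1). Control group 66, planning rates 16.6% and 67%, one-sided alpha 0.025, and the 43.4% test rate at which the plan states 81% power (10.6.2). Five strata (10.6.3). Up to 25 sites (5.1). Patients lost before 30 days count as MAE (10.2), so all 97 are analysed. The number of control sites is not given.

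**Plan's own figure.** Exact power of a one-sided Fisher test, 97 at 43.4% against 66 at 67%, is 80.99%, which reproduces the 81%.

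**Fewest possible sites.** Section 4.3 states "An investigational site may not enroll more than 20% of the total Trial Phase enrollment". 20% of 97 is 19.4, so at most 19 patients per site; 5 x 19 = 95 < 97, so at least six sites. The synopsis applies the 20% to total enrollment: 20% of 122 is 24.4, so at most 24; 4 x 24 = 96 < 97, so at least five. A pseudo-site no larger than the largest site cannot go below these counts.

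**Chance that every test cell is usable.** For a cell of n patients with MAE rate p, independent outcomes and the same rate in every cell, P(unusable) = p^n + (1-p)^n.

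| n | p = 0.166 | p = 0.434 |
|---|---|---|
| 3 | 0.585 | 0.263 |
| 4 | 0.485 | 0.138 |

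Five balanced sites by five strata give 22 cells of 4 and 3 cells of 3 (88 + 9 = 97):

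- at 16.6%: (1-0.485)^22 x (1-0.585)^3 = 3e-8, with 12.4 of 25 cells expected to be unusable;
- at 43.4%: (1-0.138)^22 x (1-0.263)^3 = 1.5%, with 3.8 of 25 expected to be unusable.

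The log of the usable probability is concave in cell size, so with every cell occupied the balanced layout is the best case. Other balanced layouts:

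| Sites | Strata | 16.6% | 43.4% |
|---|---|---|---|
| 6 | 5 | 2e-11 | 0.03% |
| 5 | 4 | 2e-5 | 17% |
| 5 | 3 | 0.4% | 62% |
| 6 | 3 | 0.02% | 33% |

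With six sites, quintiles, random stratum membership and empty cells dropped, simulation gave 0 usable trials of 40,000 at 16.6% and 0.002% at 43.4%. With 25 sites there are 125 possible cells for 97 patients (0.78 each). At 16.6%, on average 67 of 73 non-empty cells are unusable and 52 hold one patient.

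**Controls.** Assuming 2, 3 or 5 balanced control sites, the chance that all control quintile cells are usable at 67% is 47%, 5% or 9e-7. The test cells alone already defeat the quintile version.

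**Chance of entering the branch with identical sites** (simulated, 97 patients, 5 to 25 equal sites, P < 0.15):

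- Wald: 4.8% (5 sites), 2.7% (6) and 0.1% (10) at MAE 16.6%; 13%, 12% and 5% at 43.4%; near zero with 25 sites at either rate;
- score: 12-15%;
- likelihood ratio: 16-41%.

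Real site differences raise all of these.

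**Does the repair matter?** I compared three tests: half an event added to all cells, half an event added to unusable cells only, and the stratum-only test with no site weighting. The settings were six test sites, 3, 5 or 10 control sites (assumed), and stratum weights proportional to n_ic n_it/(n_ic+n_it) (assumed), not conditioned on the branch. At 16.6% against 67% all three rejected in every simulated trial. At 43.4% against 67% they disagreed in 6-9% of trials.

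**The case against.** The strongest defence is that the defect sits in a conditional branch, that the branch may seldom be entered, and that at the planned effect it would not change the answer. Much of this stands. Under a Wald test, chance entry with identical sites can be close to zero. Section 10.3 refers unspecified algorithms to the software default, although the documents do not say which test that implies. At the planning rates any sensible repair rejects the null. Simply dropping the 0% and 100% cells gives far more conflict with the other repairs, but that repair left an arm with no cells in some stratum in 19-34% of trials at 16.6%. Its results also rest on assumed weights and control-site numbers, so I do not rely on it.

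Three stronger readings are tempting, and the documents do not support them:

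- A reader might infer from "If the P-value from either test above is less than a one-sided 0.025" that the sponsor may use whichever test is favourable. The first test applies without site heterogeneity and the second with it, so the natural meaning is whichever applies.
- A reader might conclude that the main z-statistic in 10.6.4 rejects whatever the data. As it reads in the text, the 3/16 term equals (3/16) x 97/2 = 9.09, because n_ic n_it/(n_ic+n_ic) = n_it/2, and it is subtracted from a difference of proportions that cannot exceed 1. A lost inverse or operator could explain that, so it supports a check of the original page and no error rate.
- A reader might infer that the safety conclusion is in doubt at the planned rates. The comparison above shows otherwise.

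What the defence does not supply is a value for the statistic, or a rule, once the branch is entered.

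**Conclusion.** The concern holds. The site-adjusted primary safety test is undefined for cells at 0% or 100% MAE, nothing in 10.4, 10.6.3 or 10.6.4 deals with them, and with quintiles a usable statistic is practically impossible: at best 3e-8 at 16.6% and 1.5% at 43.4% with five balanced sites, and 2e-11 and 0.03% with six. These figures rest only on 97 patients, five strata, the site cap, and independent outcomes at a common rate. They do not depend on the unknown number of control sites.

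How often this would matter is less certain. Chance entry ranges from about 0% to 41% according to the logistic test used. The effect of the repair is nil at the planned effect and modest near 43.4% against 67%, under assumed weights and control-site counts. The point is that a confirmatory test must have a value in every branch the plan can reach.

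**What to change.** Before MAE data are seen, amend 10.5 and 10.6.4 as follows.

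1. Make the propensity-stratified test the primary safety test whatever the site P-value. State weights that sum to 1, for example n_ic n_it/(n_ic+n_it) normalized, and take sums over the strata actually used (5, 4 or 3).
2. Delete the stratum-by-site inverse-variance weighting for safety. Report site variation from the test-arm multivariable model already in 10.6.4.
3. If a site adjustment is kept instead, prespecify one that is defined when a cell or site has 0% or 100% events, and name the logistic test that triggers it.
4. Make the same correction to the site-weighted performance-goal test in 10.6.4. There W_k reads as (1/n_k)p_k(1-p_k), a variance and not its inverse; the inverse would be infinite for a site at 0% or 100%.
5. State that exactly one test is primary.

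Two items need checking only. Compare the main z-statistic in 10.6.4 (the 3/16 term, the repeated n_ic, the product form of w_i) with the original page, and restate it if it is printed that way. Make the synopsis, which names an exact test, agree with 10.6.4.

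The cost is text only, with no new patients or data. With identical sites and without the 3/16 term, the stratum-only test has simulated type I error of 2.6-2.7% and power of at least 99.9% at 16.6% against 67%. What is given up is the site adjustment: with an assumed between-site SD of 0.5 on the logit scale, type I error is about 4-7%. A site-weighted version with half events added did no better (7-10%). The change should be agreed with FDA, since the revision history shows that Section 10 was revised at its request.
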